# 9 Randomisation / blinding

Not Applicable, as this is an open label trial.

# 10 Prior and concomitant therapy

Patients on anticoagulant medication need to interrupt the treatment according to the recommendations of the treating physician ([name] or [name]).

All other prior or concomitant medications are allowed

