# 3 Objective of the study

To investigate whether intralaesional injection with collagenase clostridium histolyticum (XiapexR) into the stricture followed by dilation 24 hours later improves the outcome of patients with refractory gastrointestinal strictures as compared to dilation alone (standard of care).

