# 6 Introduction

The main causes of benign gastrointestinal (GI) strictures are inflammatory (eg: reflux disease, eosinophilic esophagitis, Crohn's disease, caustic...) or iatrogenic (postirradiation, post endoscopic (sub)mucosal resection, post radiofrequency ablation, anastomotic...). Most strictures respond well to endoscopic balloon dilation. Nonetheless, more than one third of patients develop recurrent symptoms after dilation within the first year (1).

In some case, the stricture can be difficult to treat and require multiple dilation sessions to obtain long-term relief of dysphagia, eating difficulties or lower GI obstructive symptoms (2, 3). A refractory stricture is defined as a cicatricial or fibrotic narrowing luminal diameter resulting in clinical symptoms of a) dysphagia (esophageal strictures), b) gastric outlet obstruction (for strictures of the stomach, pylorus, duodenum of gastrojejunal anastomosis) or c) lower GI obstruction (abdominal distension and cramps, vomiting) with an inability to successfully remediate the anatomic problem to a sufficient diameter over 3 dilation sessions at two-week intervals (4). A recurrent stricture is defined as a cicatricial or fibrotic narrowing with an inability to maintain a satisfactory luminal diameter for four weeks (4). Several options (stenting, intralesional injection of corticosteroids, needle knife incision) have been proposed to manage these strictures, with a varying success rate (5). A significant proportion of patients will finally need self-bougienage or surgery (5).

In conclusion, the treatment of GI strictures remains a challenge for clinicians and there is an unmet need for novel approaches to manage the patients suffering from this condition in order to avoid repeated dilations and/or invasive surgery.

XiapexR is a locally injectable collagenase approved for the management of Dupuytren's and Peyronie's disease (6, 7). Xiapex is a mixture of two collagenases, enzymes produced by the bacterium *Clostridium histolyticum* that dismantle collagen. Approximately 24 hours after local injection, the collagen fibres have lost their

strength and can be easily broken by manipulation. This therapy has been a breakthrough in the management of Dupuytren's disease, avoiding surgery in the vast majority of patients (6).

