# 7 The present study

## 7.1 Study design

Proof of concept open pilot study with a historical control cohort.

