## 7.3 The subjects

### 7.3.1 Number of subjects

Active group: 10 patients presenting with refractory GI strictures.

Control group: A historical cohort that consists of 40 consecutive patients that received an endoscopic balloon dilation 12-15mm for a refractory GI stricture at our centre.

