### 7.3.3 Exclusion criteria

The patient is not fluent in Dutch

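### The objective's comparator is dilation alone, but the historical controls are selected by having had a balloon dilation, and other local stricture treatment is neither screened for nor recorded in either group

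*Combined protocol and SAP*

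**What the plan says.** Section 3 asks whether the injection followed by dilation "improves the outcome of patients with refractory gastrointestinal strictures as compared to dilation alone (standard of care"). Section 7.3.4 likewise describes usual care, for patients who cannot take part, as dilation and nothing else.

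Section 7.3.1 defines the control group as "A historical cohort that consists of 40 consecutive patients that received an endoscopic balloon dilation 12-15mm for a refractory GI stricture at our centre". It sets no condition on what else was done to the stricture.

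Section 6 names alternatives to dilation: "Several options (stenting, intralesional injection of corticosteroids, needle knife incision) have been proposed to manage these strictures".

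For the prospective patients, section 10 covers the interruption of anticoagulants and then adds "All other prior or concomitant medications are allowed". The inclusion criteria (7.3.2) ask for a dilation of the same stricture in the preceding 3 months and do not mention other local treatment. The only exclusion criterion (7.3.3) is "The patient is not fluent in Dutch".

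Section 8.1 describes the review of control files as a search for outcome data. Section 12.3 plans a descriptive comparison with the historical group and mentions no separation by co-treatment.

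**The concern.** Having received a dilation is not the same as having received dilation alone. Applied as written, 7.3.1 admits a control whose index session also included a corticosteroid injection, a stent or an incision, and that patient's repeat dilations then stand for the comparator in section 3. On the active side, a patient given intralesional corticosteroid shortly before Day 0 is eligible, and any lasting effect of it would be read as part of the collagenase result.

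The design is described as "Proof of concept open pilot study with a historical control cohort". Without randomisation, comparability rests on how the controls are defined and on what is recorded about both groups. The plan provides neither for other local treatment, which could plausibly affect the primary outcome, the number of repeat dilations over 6 months. Enrolling more patients would not remove such a bias.

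**Working it through.** The plan gives no sample size calculation, effect size or adjunct rate (12.1, 12.3), so there is no figure to reproduce. The check has two parts: reading the rules together, then an illustration on assumed values.

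**Rules side by side**

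- Contrast intended: dilation alone (section 3, consistent with 7.3.4).
- Control selection: any consecutive patient with a 12-15mm dilation for a refractory stricture (7.3.1). Adjuncts at the index session are not excluded.
- Active eligibility: section 10 allows medications, which includes an injected corticosteroid. Stents and incisions are procedures. Section 10 does not allow them; they are simply not addressed there or in 7.3.2 and 7.3.3.
- Active index procedure: injection on Day 0 and balloon dilation on Day +1 (8.1, 8.2). No other local treatment is listed.
- Recording and analysis: no item for adjuncts in 8.1 or 8.2, and no display by adjunct in 12.3.

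The gap therefore lies in 7.3.1 for controls (index session and earlier), and in section 10 with 7.3.2 and 7.3.3 for active patients (earlier treatment).

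**Illustration**

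Let fA and fC be the shares of the active and control groups with an adjunct, and r the factor by which an adjunct multiplies the repeat-dilation rate. If the drug and adjunct effects multiply,

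apparent RR = true RR × (1 − fA + fA·r) / (1 − fC + fC·r).

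The documents give none of fA, fC or r. Assumed: r = 0.5 or 0.7, shares of 30% or 50%. A 30% share is 0.3 × 10 = 3 active patients or 0.3 × 40 = 12 controls.

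| True RR | Adjunct in | r=0.5, 30% | r=0.5, 50% | r=0.7, 30% | r=0.7, 50% |
|---|---|---|---|---|---|
| 1.00 | active only | 0.850 | 0.750 | 0.910 | 0.850 |
| 1.00 | controls only | 1.176 | 1.333 | 1.099 | 1.176 |
| 0.70 | active only | 0.595 | 0.525 | 0.637 | 0.595 |
| 0.70 | controls only | 0.824 | 0.933 | 0.769 | 0.824 |

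Example: controls only, r = 0.5, share 30%, true RR 0.70 gives 0.70 / (1 − 0.3 + 0.3 × 0.5) = 0.70 / 0.85 = 0.824.

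With equal use, say 30% in each group, numerator and denominator cancel and the apparent RR equals the true one.

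On the mean scale, assume 4 repeat dilations with dilation alone and 2 with an adjunct. With adjuncts in 30% of controls, the control mean is 0.7 × 4 + 0.3 × 2 = 3.4, and a true reduction of 2 shows as 3.4 − 2 = 1.4, which is 30% too small. With adjuncts in 3 of 10 active patients and an inactive drug, 3.4 against 4.0 is a false reduction of 0.6 / 4 = 15%. Over shares of 10% to 50% in one group, the shift is 0.1 × 2 = 0.2 to 0.5 × 2 = 1.0 dilations.

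These cases take r below 1. An earlier adjunct that failed may instead mark a harder stricture. Then r is above 1, and each shift reverses direction.

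**The case against.** The strongest reply is that local practice may already be dilation alone. Sections 3 and 7.3.4 both describe standard care that way, and the controls come from the same centre. This makes frequent adjuncts among controls less likely, and the 30% and 50% shares have no support in the documents. That stands as a limit on size. It does not close the gap, because 7.3.4 concerns patients who cannot take part and is not a selection rule for the cohort. If practice is as described, saying so in 7.3.1 costs almost nothing.

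Several stronger readings are tempting but not supported:

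- A reader might infer that section 10 opens both groups to all three adjuncts. It speaks of medications and governs the prospective patients. It does not reach procedures or the historical files.
- A reader might infer that the plan allows a corticosteroid injection at the Day +1 session. Sections 8.1 and 8.2 list the steps and include no such injection. It is not expressly forbidden, but reading a general medication sentence as adding a procedure is strained.
- A reader might take section 6 as evidence of practice at this centre. It says that the options have been proposed, which is literature background.
- A reader might infer that two or three such patients would decide the result. The analysis in 12.3 is descriptive, with no test or threshold to cross.

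The descriptive aim tempers the consequences but does not answer the point, since 12.3 still compares the groups.

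**Conclusion.** The point holds as a mismatch between the stated contrast and the stated cohort rule, together with missing information on earlier local treatment in both groups. Followed literally, the plan can produce a comparator that is not the one in section 3.

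It does not follow that the comparison is biased. The documents do not show that adjuncts were used or that use differed. Equal use leaves the ratio unchanged and unequal use can move it either way. Adjuncts among active patients need not flatter the drug, because earlier failed treatment may mark a worse prognosis. The size is unknown. The ranges shown (0.75 to 0.91 or 1.10 to 1.33 for an inactive drug) rest wholly on assumed shares, an assumed adjunct effect and use in one group only.

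This is a cheap improvement to a pilot, not a defect that invalidates it.

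**What to change.** - **7.3.1:** define the 40 consecutive controls as patients whose index session was balloon dilation without another local anti-stricture treatment.
- **8.1 and the CRF:** record in both groups any such treatment at the index session and in a look-back of 3 months, the window already used in the inclusion criteria. The look-back is recorded, not used to select patients, so both groups are handled alike.
- **12.3:** keep all 10 active patients in the main descriptive comparison, and add the primary outcome by adjunct status as a sensitivity display. Making an adjunct-free subset the main comparison would shrink an already small group, so it is not recommended.
- **Consistency:** sections 3, 7.3.1, 7.3.4 and 10 must be reconciled. Which co-treatments to permit is a clinical matter, and no rule on it is proposed here.

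The cost is a few lines of protocol text and one extra data item in the file review and CRF. The downside is that the search for 40 controls may have to reach further back in time.

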# 11 Adverse event reporting

#### List of abbreviations

AE	Adverse Event
CA	Competent Authority

EC Ethics Committee

SAE Serious Adverse Event

SSAR Suspected Serious Adverse Reaction

SUSAR Suspected Unexpected Serious Adverse Reaction

### Adverse events (AE)

The following information will be recorded:

- nature of adverse event
- date and time of occurrence and disappearance
- intensity: mild, moderate or severe
- frequency: once, continuous or intermittent
- decision regarding study: continuation or withdrawal
- relation to the study medication (see below)

AE's will be recorded from the first drug administration until the end of the trial. Special attention will be given to those subjects who have discontinued the trial for an AE, or who experienced a severe or a serious AE.

### Definitions of Adverse Event (AE)

Any untoward medical occurrence in a patient or clinical investigation subject administered a pharmaceutical product and which does not necessarily have a causal relationship with this treatment. An adverse event (AE) can therefore be any unfavorable and unintended sign (including an abnormal finding), symptom, or disease temporally associated with the use of a medicinal (investigational) product, whether or not related to the medicinal (investigational) product.

#### Serious Adverse Avent (SAE)

Any untoward medical occurrence that at any dose:

- results in death
- is life-threatening
- requires inpatient hospitalization or prolongation of existing hospitalization,
- results in persistent or significant disability/incapacity,
- or

- is a congenital anomaly/birth defect.

Note: Medical and scientific judgment should be exercised in deciding whether expedited reporting is appropriate in other situations, such as important medical events that may not be immediately life-threatening or result in death or hospitalization but may jeopardize the subject or may require intervention to prevent one of the outcomes listed in the definition above.

#### Unexpected adverse event

An adverse event, the nature or severity of which is not consistent with the applicable product information (e.g., Investigator's Brochure for an unapproved investigational product or package insert/summary of product characteristics for an approved product).

### Life-threatening

Any event in which the subject was at risk of death at the time of the event; it does not refer to an event which hypothetically might have caused death if it were more severe.

#### Associated with the use of the drug

An adverse event is considered associated with the use of the drug if the attribution is possible, probable or definitive.

### Attribution definitions

### Not related

An adverse event which is not related to the use of the drug.

### Unlikely

An adverse event for which an alternative explanation is more likely - e.g. concomitant drug(s), concomitant disease(s), and/or the relationship in time suggests that a causal relationship is unlikely.

### Possible

An adverse event which might be due to the use of the drug. An alternative explanation - e.g. concomitant drug(s), concomitant disease(s), - is inconclusive. The relationship in time is reasonable; therefore the causal relationship cannot be excluded.

### Probable

An adverse event which might be due to the use of the drug. The relationship in time is suggestive (e.g. confirmed by dechallenge). An alternative explanation is less likely - e.g. concomitant drug(s), concomitant disease(s).

### Definitely

An adverse event which is listed as a possible adverse reaction and cannot be reasonably explained by an alternative explanation - e.g. concomitant drug(s), concomitant disease(s). The relationship in time is very suggestive (e.g. it is confirmed by dechallenge and rechallenge).

#### Reporting of adverse events

Adverse events will be reported between the first dose administration of trial medication and the last trial related activity.

All AEs and SAE's will be recorded in the patient's file and in the CRF. All SAE's will be reported as described below.

Medical events that occur between signing of the Informed Consent and the first intake of trial medication will be documented on the medical and surgical history section and concomitant diseases page of the CRF.

SAE's occurring within a period of 30 days following the last intake of trial medication will also be handled as such if spontaneously reported to the investigator.

All serious adverse events (SAE) and pregnancies occurring during clinical trials must be reported by the Principal Investigator within 2 working days after becoming aware of the SAE to:

- HIRUZ of the University Hospital Ghent. HIRUZ will submit the finalized report to the Central Ethics Committee.

This reporting is done by using the appropriate SAE form. For the contact details, see below.

It is the responsibility of the local Principal Investigator to report the local SAE's to the local EC.

In case the investigator decides the SAE is a SUSAR (Suspected Unexpected Serious Adverse Reaction), HIRUZ will report the SUSAR to the Central EC and the CA within the timelines as defined in national legislation. The National Coordinating Investigator reports the SUSAR to all local Principal Investigators.

In case of a life-threatening SUSAR the entire reporting process must be completed within 7 calendar days. In case of a non life-threatening SUSAR the reporting process must completed within 15 calendar days.

The first report of a serious adverse event may be made by telephone, e-mail or facsimile (FAX).

Contact details of the Health, innovation and research institute (HIRUZ):

e-mail: [contact] [contact] [contact]

Contact details of the Principal Investigator: e-mail: [contact] tel.: In hospital: [name]; cellphone [name] [contact]

The investigator must provide the minimal information: i.e. trial number, subject's initials and date of birth, medication code number, period of intake, nature of the adverse event and investigator's attribution.

This report of a serious adverse event by telephone must always be confirmed by a written, more detailed report. For this purpose the appropriate SAE form will be used. Pregnancies occurring during clinical trials are considered immediately reportable events. They must be reported as soon as possible using the same SAE form. The outcome of the pregnancy must also be reported.

All subjects will receive a "trial card" indicating the name of the investigational product, the trial number, the investigator's name and a 24-hour emergency contact number.

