## 7.3.5 Restrictions and prohibitions for the subjects

- Patient need fasting for at least 8 hours prior to the gastroscopies
- Patients on anticoagulant medication need to interrupt the treatment according to the recommendations of the treating physician ([name] or [name])

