### 7.3.6 Possible advantages and risks for the subjects

It is possible that participation to the study will result in less need for repeat dilations for a refractory upper GI stricture (unknown).

Every dilation carries the risk of perforation, even in the most experiences hands. No additional dilations are performed in light of the study. It is unknown whether local injection of the study drug augments the risks of perforation. Every patient is carefully monitored after dilation (standard of care). Upon clinical suspicion of perforation, a CT scan is performed for confirmation.

suspicion of perforation, a CT scan is performed for confirmation. In case of confirmed perforation, endoscopic stenting is immediately performed to bridge the defect, allowing healing of the defect. The stent can most of the time be removed after 6 weeks. In some case, endoscopic clipping is the treatment of choice to close the iatrogenic perforation. Surgical intervention is seldomly needed

Side effects of the study drug (XiapexR) are expected to be very limited, as the study drug does not enter the bloodstream in significant amounts and is rapidly degraded in the bloodstream by proteases. Local reactions (bleeding, swelling, inflammation) are theoretically possible. Like all foreign substances, Xiapex can induce allergic reactions but these seem to be very rare (only 1 case described in literature).

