## 8.2 Flowchart

- Between day -7 to day -1: Informed consent

- Day 0: Endoscopy, xiapex injection into the strictures (4 quadrants, 0.75ml or 0.25mg per quadrant)
- Day +1: Endoscopy, CRE balloon dilation 12mm to max 15mm
- Day +2 to month 2: clinical evaluation (by phone) every 2 weeks with a window of 3 days (see above for primary and secondary outcome measures)
- Month 2-month 6: Clinical evaluation (by phone) every 4 weeks with a window of 3 days (see above for primary and secondary outcome measures)

The expected total duration of the trial is 18 months.

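### Adverse event recording opens at the injection, so harm from a study procedure before dosing is classed as medical history, and whether a serious pre-dose event must be reported is unclear

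*Combined protocol and SAP*

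**What the plan says.** Section 11 states the AE window twice. Under Adverse events (AE): "AE's will be recorded from the first drug administration until the end of the trial". Under Reporting of adverse events: "Adverse events will be reported between the first dose administration of trial medication and the last trial related activity". The second subsection then deals with the time between consent and first dose: "Medical events that occur between signing of the Informed Consent and the first intake of trial medication will be documented". It also names the place, in that such events "will be documented on the medical and surgical history section and concomitant diseases page of the CRF". The AE definition points the same way, since it begins "Any untoward medical occurrence in a patient or clinical investigation subject administered a pharmaceutical product". The list of items to record for each AE asks about relation to the study medication and has no item for relation to a study procedure.

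Reporting of adverse events also requires the principal investigator to report all SAEs and pregnancies arising during the trial within 2 working days. That sentence names no starting point.

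Section 8.2 places consent between Day -7 and Day -1, followed by "Day 0: Endoscopy, xiapex injection into the strictures". Under section 8.1 the standard-of-care dilation takes place at a second endoscopy 24 hours later. Section 7.3.6 says "No additional dilations are performed in light of the study" and does not mention the added endoscopy. Sections 7.3.5 and 10 say: "Patients on anticoagulant medication need to interrupt the treatment according to the recommendations of the treating physician", without giving the timing. Section 4 lists complication rate as a secondary outcome, with no definition or time window.

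**The concern.** The experimental strategy is more than the drug. It is an extra endoscopy to inject, followed a day later by the dilation that the patient would have had anyway. A safety description of that strategy should cover the whole of the added step. Under section 11, an event during preparation, passage of the scope or approach to the stricture on Day 0 comes before the first administration and goes to the history pages. Those pages carry no stated requirement for severity, causality or expedited reporting. If the endoscopy is started and the injection is then abandoned, perhaps because of a complication, there is no first administration and AE recording never opens for that patient.

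Two things are at stake. One is whether a serious event of this kind reaches the sponsor's reporting unit in time. The other is whether the complication rate, in a first evaluation of this drug in refractory GI strictures, reflects all harm from the added step.

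**Working it through.** The plan gives no figure to reproduce; section 12.1 states that no sample size calculation was made. The check is mainly a comparison of texts.

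**1. The window set against the schedule**

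| Period | What the study does | Class under section 11 |
|---|---|---|
| Consent (Day -7 to Day -1) up to Day 0 | Anticoagulant interruption, if it falls here (timing not stated) | History or concomitant disease |
| Day 0, before the needle | Endoscopy added for the injection | History or concomitant disease |
| Day 0, endoscopy started, injection abandoned | Same endoscopy, no dose given | AE window never opens |
| Day 0, after the injection | Rest of the same endoscopy | AE |
| Day +1 onward | Dilation, then telephone follow-up to month 6 | AE |

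The gap lasts 1 to 7 days per patient plus the pre-injection part of one endoscopy. For 10 patients the days before Day 0 come to between 10 × 1 = 10 and 10 × 7 = 70 patient-days. In a patient not taking anticoagulants, the main study procedure in the gap is the pre-injection part of Day 0.

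**2. The two rules for a serious pre-dose event**

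The window sentences, the history-page sentence and the AE definition together say that it is not an AE, and hence not an SAE. The 2-working-day sentence, read alone, covers any SAE arising during the trial. A site could follow either, and nothing says which prevails.

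**3. Scale, for illustration only**

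Assume that the complication rate is taken from AE records. With n = 10, exact (Clopper-Pearson) two-sided 95% limits are:
- One event counted: 1/10 = 10%, limits 0.3% to 44.5%.
- The same event classed as history: 0/10, upper limit 1 − 0.025^(1/10) = 30.8%.

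The documents give no pre-dose event risk. Taking an assumed risk p, equal for all patients, the chance of at least one such event among 10 is 1 − (1 − p)^10:

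| Assumed p | Chance of at least one event |
|---|---|
| 0.5% | 4.9% |
| 1% | 9.6% |
| 2% | 18.3% |
| 5% | 40.1% |

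These values of p are assumptions chosen to show a range. They are not estimates for this population.

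**The case against.** The strongest reply is that section 11 is consistent about when AE recording starts, that opening it at first dose is a design choice, and that little is lost in a descriptive pilot of 10 patients. Much of this stands, and it rules out several stronger readings that a reader might infer.

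- *That pre-dose harm is lost from the data.* It is not. Such events must be entered in the CRF and could be listed. They are misclassified rather than unrecorded.
- *That harm from the Day 0 endoscopy as a whole is excluded.* The injection is given during that endoscopy, so any complication arising after the injection is an AE. So is harm from anticoagulant interruption that appears after dosing.
- *That harm from anticoagulant interruption belongs to the study.* The Day +1 dilation is standard of care, and the interruption is left to the treating physician. The documents do not say whether dilation alone would have required it, or whether the extra endoscopy lengthens it.
- *That SAE reporting is blocked.* The 2-working-day sentence leaves room to report a serious pre-dose event. The text is contradictory, not prohibitive.
- *That the complication rate is biased in favour of the active group.* The outcome has no stated window or link to AE records, and the controls' outcomes come from patient files with no stated AE window. A distortion is possible but not established.

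The first-dose start is still more than missing detail. It is an explicit rule that classes harm from a study-specific procedure as medical history, it makes no provision for an abandoned injection, and it conflicts with another sentence in the same subsection.

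**Conclusion.** The point holds in a limited form. An event caused by a study procedure before dosing, chiefly in the pre-injection part of the added Day 0 endoscopy or in an endoscopy where the injection is abandoned, is recorded in the CRF but not classed as an AE. No causality assessment against study procedures is required at any time. Whether a serious pre-dose event must be reported within 2 working days cannot be settled from the text. Harm from anticoagulant interruption before Day 0 falls in the same gap, whether or not the study is its cause.

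The exposure is short and the expected number of events is unknown. The effect on the complication rate depends on the assumption that this outcome will be built from AE records; if so, a single event separates 1/10 from 0/10. The change is worth making because it is cheap and removes a contradiction in safety reporting, not because a bias has been shown.

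**What to change.** 1. In section 11, under both Adverse events (AE) and Reporting of adverse events, state that from signed consent all SAEs, and all AEs related to a study-required procedure or treatment interruption, are recorded and reported as AEs or SAEs. Keep the history and concomitant-disease pages for other, unrelated pre-dose events.
2. Reconcile the 2-working-day SAE sentence and the AE definition with that start, so that one rule applies to serious pre-dose events.
3. Add relation to study procedure to the list of items recorded for each AE, beside relation to study medication.
4. State that every patient who starts the Day 0 endoscopy counts in the complication-rate denominator, whether or not the injection is given.

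The cost is a short amendment to section 11, one added CRF item, one sentence on the denominator, and at most about one week of extra AE recording for each of 10 patients. The active complication rate may come out slightly less favourable.
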